1 PROTOCOL SUMMARY

1.1 SYNOPSIS

Title:	A Randomized, Single-Blinded, Sham-Controlled Study Evaluating the Efficacy and Safety of RELAY, a Device Enabling Both Local Anesthetic Delivery and Neuromodulation for Postoperative Analgesia, in Participants Having Shoulder or Foot Surgery Following a Single-Arm Training Run-In.
Study Description:	
This is a single-center, sham-controlled study to investigate the efficacy and safety of RELAY, a device that enables the delivery of both local anesthetic and neuromodulation (peripheral nerve stimulation) to treat postoperative pain.
 
RELAY is comprised of a basic catheter-over-needle device to allow administration of a single-injection of local anesthetic via the needle (or catheter) followed by a perineural local anesthetic infusion via the remaining catheter (when desired). Subsequent to the local anesthetic administration, instead of removing the catheter as with all previous continuous peripheral nerve block equipment, electric current may be delivered via the same catheter for up to a total of 28 days. This is potentially paradigm shifting because it would allow an anesthesiologist to deliver (1) a single-injection peripheral nerve block; (2) a continuous peripheral nerve block; and (3) neuromodulation using a single device that can theoretically be placed in the same amount of time required for a single-injection peripheral nerve block. Instead of providing fewer than 24 hours of postoperative analgesia, up to 28 days of pain control could be delivered without disruption of the existing practice patterns.
 
Following a training run-in period, the randomized single blind sham-controlled part of the study will commence. The purpose of the training run-in period is to ensure that RELAY can be safely placed next to a target nerve, successfully programmed and induce peripheral nerve block and neuromodulation based on the instructions for use. This will ensure familiarity with the device prior to the randomized portion of the study. The training period will consist of up to 20 participants (~ 5 to 10 catheter lead insertions per anesthesiologist) across at least two different surgical procedures.
 
It is anticipated that during the training run-in phase, the successful deployment of the RELAY system will be achieved 80% or more of the time. If less than 80% is achieved, the study will not proceed to the randomized portion. A brief study report will be submitted to the FDA prior to initiating the randomized portion.
 
RELAY deployment success will be defined as a successfully placed catheter/lead as evidenced by sensory changes in the distribution of the target nerve with (1) electrical stimulation eliciting paresthesia and (2) inducing a conduction nerve block with injection of local anesthetic injection leading to either decreased or absent sensation to cold with alcohol swab.
 
The randomized portion will include 40 participants (with up to 10 additional participants to account for drop-outs) randomized (1:1) to the experimental and sham arms, respectively. A futility analysis will be performed once 20 participants have been randomized and data through post-operative Day 7 are available. The following two criteria must be achieved to move forward: 1) RELAY deployment success in the lead/catheter insertion of $\geq 85\%$ in RELAY participants, and 2) a conditional power


	(Cp) of $\geq 30\%$ for the primary efficacy endpoint. Of note, a standardized effect size of 0.49 would not meet criteria to continue. There will be no stopping for early efficacy.
Objectives/ Endpoints	
The primary objective of the proposed research study is to assess postoperative analgesia that extends beyond the duration of the local anesthetic interventions to prepare for a subsequent pivotal definitive clinical trial with the RELAY device compared to sham control.
 
Primary endpoint: Difference in the average daily pain intensity for Days 1-7 as measured with the Numeric Rating Scale (NRS) within the Brief Pain Inventory (BPI) via the RELAY device compared to sham control.
 
• Hypothesis 1: Neuromodulation with the RELAY device will decrease average pain intensity for Days 1-7 following foot and shoulder surgery currently treated with a single-injection peripheral nerve block (as measured with the NRS within the BPI). 
The key secondary objectives are:
 
1) To estimate the effect on opioid consumption of neuromodulation via the RELAY device as compared to sham control 
Key secondary endpoint 1 (hierarchical: tested for significance only if the primary endpoint achieves significance at alpha 1-sided <0.025): Difference in the cumulative opioid use (oxycodone equivalents) for Days 1-7 via the RELAY device compared to sham control.
 
• Hypothesis 2: Neuromodulation with the RELAY device will decrease opioid consumption within the week following foot and shoulder surgery currently treated with a single-injection peripheral nerve block (measured in oxycodone equivalents), as measured both with daily and cumulative opioid consumption within the first postoperative week). 
2) To estimate the effect on physical and emotional functioning of neuromodulation via the RELAY device as compared to sham control 
Key secondary endpoint 2 (hierarchical: tested for significance only if the primary endpoint and key secondary endpoint 1 both achieve significance at alpha 1-sided <0.025): Difference in BPI interference subscale on Day 3 as measured with the NRS within the BPI Inventory via the RELAY device compared to sham control.
 
• Hypothesis 3: Neuromodulation with the RELAY device will decrease pain's interference in physical and emotional functioning within the week following foot and shoulder surgery currently treated with a single-injection peripheral nerve block (as measured with the Interference Subscale of the BPI). 
Other Secondary Endpoints to include:
 
• Interference in physical and emotional functioning (as measured with the Interference Subscale of the BPI) on Post-op Day 7• Opioid use (oxycodone equivalents) on Post-op Days 1, 2, 3, 4, 7, 8 and 14• Awakenings due to pain on Post-op Days 1, 2, 3, 4, 7, 8 and 14

[figure not shown]
	
 • Daily Pain intensity (“average” and “worst” NRS) on Post-op Days 1, 2, 3, 4, 7, 8, 14 • Daily Pain intensity (“current” and “least” NRS) on Post-op Days 3 and 7 • Frequency, pulse duration, amplitude, and anode (proximal vs distal) will be recorded at baseline; amplitude during postoperative Days 1, 2, 3, 4, and 7 • Masking assessment on Post-op Day 1 (randomized period only) 																																																								
Post-Enrollment Assessments	
Summary of post-enrollment assessments (color added for clarity)
 
  
 Postoperative Day:	1	2	3	4	7	8	14	
   
 Opioid consumption	•	•	•	•	•	•	•	
 
 Average Pain [Numeric Rating Scale; as part of the Brief Pain Inventory]	•	•	•	•	•	•	•	
 
 Worst Pain [Numeric Rating Scale; as part of the Brief Pain Inventory]	•	•	•	•	•	•	•	
 
 Brief Pain Inventory			•				•	
 
 Awakenings from sleep due to pain	•	•	•	•	•	•	•	
 
 Masking Assessment (randomized period only)	•							
  
	Postoperative Day:	1	2	3	4	7	8	14	Opioid consumption	•	•	•	•	•	•	•	Average Pain [Numeric Rating Scale; as part of the Brief Pain Inventory]	•	•	•	•	•	•	•	Worst Pain [Numeric Rating Scale; as part of the Brief Pain Inventory]	•	•	•	•	•	•	•	Brief Pain Inventory			•				•	Awakenings from sleep due to pain	•	•	•	•	•	•	•	Masking Assessment (randomized period only)	•						
Postoperative Day:	1	2	3	4	7	8	14																																																		
Opioid consumption	•	•	•	•	•	•	•																																																		
Average Pain [Numeric Rating Scale; as part of the Brief Pain Inventory]	•	•	•	•	•	•	•																																																		
Worst Pain [Numeric Rating Scale; as part of the Brief Pain Inventory]	•	•	•	•	•	•	•																																																		
Brief Pain Inventory			•				•																																																		
Awakenings from sleep due to pain	•	•	•	•	•	•	•																																																		
Masking Assessment (randomized period only)	•																																																								
Study Population	
There will be approximately 70 participants.
 
Inclusion criteria:
 
 1. Adult participants of at least 18 years of age 2. Undergoing a rotator cuff repair, total shoulder arthroplasty, hallux valgus correction or ankle arthroplasty/arthrodesis 3. Planned single-injection peripheral nerve block(s) 4. An Android or Apple smartphone able to download the Gate Keeper controller app 
Exclusion criteria:
 
 1. Chronic opioid or tramadol use (daily within prior 2 weeks and duration > 4 weeks) 2. Neuro-muscular deficit of the surgical limb 3. Compromised immune system based on medical history (e.g., immunosuppressive therapies such as chemotherapy, radiation, sepsis, infection), or other conditions that places the subject at increased risk of infection 4. Implanted spinal cord stimulator, cardiac pacemaker/defibrillator, deep brain stimulator, or other implantable neurostimulator whose stimulus current pathway may overlap 5. History of bleeding disorder 6. Antiplatelet or anticoagulation therapies other than aspirin 7. Allergy to skin-contact materials (occlusive dressings, bandages, tape etc.) 8. Incarceration 																																																								

	
 9. Pregnancy 10. Moderate pain (NRS > 3) in an anatomic location other than the surgical site 11. Anxiety disorder 12. History of substance misuse 13. Inability to communicate with the investigators 14. Inability to contact the investigators during the treatment period, and vice versa (e.g., lack of telephone access) 15. Allergy to amide local anesthetics 16. Morbid obesity (body mass index > 40 kg/m²)
Phase:	Not applicable to this investigation involving a medical device (as opposed to a medication)
Description of Sites/Facilities Enrolling Participants	U.C. San Diego Clinical and Translational Research Institute and hospitals (including the ambulatory surgical centers)
Description of Study Intervention	
The RELAY system combines a catheter-over-needle to permit ultrasound-guided percutaneous insertion with the tip adjacent to a peripheral nerve or plexus, followed by needle removal which leaves the catheter in situ to deliver a bolus of local anesthetic (if desired) and subsequent perineural local anesthetic infusion (if desired). The catheter also has 3 integrated electrodes to enable neuromodulation using the integrated pulse generator and battery (figure below).
  
Participants will have standard external monitors placed and oxygen delivered by facemask or nasal cannula. The peripheral nerve block site(s) will be cleansed with chlorhexidine gluconate and isopropyl alcohol. Intravenous sedation/analgesia with midazolam and/or fentanyl will be titrated for patient comfort as is standard for peripheral nerve block administration. The nerves treated will include the sciatic proximal to the popliteal crease for foot surgery and the brachial plexus for shoulder surgery. The target nerve(s) will be visualized with ultrasound using a transverse cross-sectional (short axis) view and a skin wheal of local anesthetic will be raised inferior to the transducer to anesthetize the skin and then the track towards the target.

	
Treatment group allocation (randomization). Participants in the training run-in period will all receive active neuromodulation. Participants in the randomized portion will be randomized (1:1) to one of two possible treatments groups:
 
○ Neuromodulation (Active)○ Sham (Control) 
Randomization will be stratified by anatomic location (shoulder and foot/ankle surgery) in a 1:1 ratio and in blocks of 2. Computer-generated randomization lists will be created by the UC San Diego Investigational Drug Service and the allocation provided to the investigators via sequential, opaque envelopes.
 
Pulse generators are available that are capable of either (1) passing electrical current; or (2) not passing electrical current. Importantly, these 2 modes (active and sham) are indistinguishable in appearance, and therefore investigators, participants, and all clinical staff will be masked to treatment group assignment, with the only exception being the unmasked individuals who insert the RELAY and program the stimulator.
 
The RELAY system with the integrated needle will be inserted adjacent to the target nerve with an in-plane approach. Dextrose 5% in water (1-20 mL) will be injected via the needle to open a space around the target nerve(s), the catheter advanced, and the needle subsequently withdrawn.
 
Active (neuromodulation) group. For participants receiving active (neuromodulation) treatment, electrical current will be introduced with increasing intensity via each of the anode electrodes to optimize participant's perceived stimulation (control provided by the Gate Keeper app from an investigator's phone or tablet). Accurate lead placement will be confirmed with subject reports of comfortable sensations over the surgical site without eliciting muscle contractions. The minimum threshold and maximum comfortable amplitudes will be determined along with the optimal frequency, pulse duration, and anode/cathode. Starting from the lowest possible current the current will be increased until a participant states that they feel a "buzzing" sensation (some describe it as a "comfortable massage"). That is the minimal sensed current. The current will then continue to be increased with instruction to the participant to let the investigator know when it starts to be less comfortable—and to stop the investigator before it hurts. That is the maximum comfortable current. The stimulator will then be set to deliver the minimum threshold amplitude and turned off for surgery.
 
Sham (control) group. For participants receiving sham treatment, electric current will not reach the anodes, but the investigators will connect the RELAY to the Gate Keeper app just as with the active group and set the parameters as follows: anode (distal), cathode (proximal), frequency (100 Hz), pulse duration (100 μs), and amplitude (5 mA).
 
Local anesthetic for active and sham groups. Local anesthetic (10 mL of lidocaine 2% with epinephrine) will be injected with negative aspiration every 3 mL and resulting sensory block confirmed to ensure accurate catheter tip placement. Following block confirmation (sensory deficits in the expected nerve distributions), the RELAY system will be affixed with both surgical adhesive (2-Octyl 2-cyanoacrylate) at the entry site and a chlorohexidine-impregnated occlusive dressing. Subsequently, 10 mL of bupivacaine 0.5% with epinephrine will be injected negative aspiration every 3 mL

--	--

	
along with a supplemental single-injection saphenous nerve block for foot/ankle surgery.
 
Intraoperatively, surgeons will be permitted to infiltrate the surgical area with long-acting local anesthetic as their common practice dictates.
 
Postoperatively, the stimulators will be connected to participants' phones and turned on.
 
For the training run-in period, if a patient's surgeon requests a postoperative continuous peripheral nerve block, a ropivacaine 0.2% infusion will be provided per standard UC San Diego protocol.
 
After 7 days, participants in both the active and sham groups, themselves or their caretaker will remove the occlusive dressing and withdraw the catheter (and integrated electrodes) with gentle traction and rotation at home. The devices are single-use and disposable.

Study Duration:	Approximately 12 months
Participant Duration:	Approximately 2 weeks

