3 OBJECTIVES AND ENDPOINTS

OBJECTIVES	ENDPOINTS	JUSTIFICATION FOR ENDPOINTS
Primary		
To assess postoperative analgesia that extends beyond the duration of the local anesthetic interventions to prepare for a subsequent pivotal definitive clinical trial with the RELAY device as compared to sham control.	Difference in the average daily pain intensity for Days 1-7 as measured with the NRS within the BPI between the RELAY device and sham control arms.	Pain negatively influences physical and emotional functioning.
Key Secondary		
To estimate the effect on opioid consumption of neuromodulation via the RELAY device as compared to sham control	Neuromodulation with the RELAY device will decrease cumulative opioid consumption during the first postoperative week following foot and shoulder surgery currently treated with a single-injection peripheral nerve block (measured in oxycodone equivalents).	Opioid use has negative individual and society consequences
To estimate the effect on physical and emotional functioning of neuromodulation via the RELAY device as compared to sham control	The physical and emotional functioning of participants will be improved on postoperative Day 3 following foot and shoulder surgery currently treated with a single-injection peripheral nerve block (as measured with the BPI Interference Subscale)	Pain negatively influences physical and emotional functioning.
Other Secondary		
To estimate the effect on physical and emotional functioning of neuromodulation via the RELAY device as compared to sham control	The physical and emotional functioning of participants will be improved on postoperative Day 7 following foot and shoulder surgery currently treated with a single-injection peripheral nerve block (as measured with the BPI Interference Subscale)	Pain negatively influences physical and emotional functioning.
To estimate the analgesic effect of neuromodulation via the RELAY device as compared to sham/placebo for the RELAY device following foot and shoulder surgical procedures at various time points post-treatment	Neuromodulation with the RELAY device will decrease pain intensity (as measured by the “average” and “worst” (maximum) daily NRS within the BPI) on Days 1, 2, 3, 4, 7, 8, and 14 following foot and shoulder surgery currently treated with a single-injection peripheral nerve block.	Pain negatively influences physical and emotional functioning.

OBJECTIVES	ENDPOINTS	JUSTIFICATION FOR ENDPOINTS

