To estimate the analgesic effect of neuromodulation via the RELAY device as compared to sham/placebo for the RELAY device following foot and shoulder surgical procedures at various time points post-treatment	Neuromodulation with the RELAY device will decrease pain intensity (as measured by “current” and “least” daily NRS within the BPI) on Days 3 and 7 following foot and shoulder surgery currently treated with a single-injection peripheral nerve block.	Pain negatively influences physical and emotional functioning.
To estimate the effect on opioid consumption of neuromodulation via the RELAY device as compared to sham/placebo for the RELAY device following foot and shoulder surgical procedures at various time points post-treatment	Neuromodulation with the RELAY device will decrease daily opioid consumption following foot and shoulder surgery currently treated with a single-injection peripheral nerve block (measured in oxycodone equivalents on Days 1, 2, 3, 4, 7, 8 and 14).	Opioid use has negative individual and society consequences
To estimate the effect on sleep disturbances of neuromodulation via the RELAY device as compared to sham/placebo for the RELAY device following foot and shoulder surgical procedures at various time points post-treatment	Neuromodulation with the RELAY device will decrease cumulative awakenings due to pain following foot and shoulder surgery currently treated with a single-injection peripheral nerve block (evenings of postoperative Days 1, 2, 3, 4, 7, 8 and 14)	Poor sleep quality is correlated with inferior analgesia and functioning
To evaluate the masking quality of the study protocol	The masking assessment on Post-op Day 1	Successful masking reduces bias

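### The synopsis assessment table marks the full Brief Pain Inventory on Days 3 and 14, but the endpoints that depend on it need Days 3 and 7

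*Combined protocol and SAP*

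**What the plan says.** **The schedule.** The post-enrollment assessment table in Section 1.1 has seven day columns: "Postoperative Day: 1 2 3 4 7 8 14". Average pain and worst pain have their own rows, marked on all seven days. The full instrument has a separate row, "Brief Pain Inventory", with two marks, in the Day 3 and Day 14 cells. The Day 7 cell is empty.

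**The endpoints.** The other secondary endpoints in Section 1.1 include:

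- "Interference in physical and emotional functioning (as measured with the Interference Subscale of the BPI) on Post-op Day 7"
- "Daily Pain intensity (“current” and “least” NRS) on Post-op Days 3 and 7"

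Section 3 repeats the first ("The physical and emotional functioning of participants will be improved on postoperative Day 7 following foot and shoulder surgery") and the second ("as measured by “current” and “least” daily NRS within the BPI) on Days 3 and 7"). In the serial testing table of Section 9.4.3, set 3 is BPI interference on Day 3 and set 5 is BPI interference on Day 7.

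**Where the items come from.** Section 8.1 takes current, least, worst and average pain from the BPI short form, and interference from the seven-question scale of the same instrument. It gives Days 1, 2, 3, 4, 7, 8 and 14 as the general evaluation days but does not say which instrument is used on which day.

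**The concern.** An assessment schedule is what callers and form designers work from. In the synopsis table, interference, current pain and least pain have no rows of their own, so they are collected only when the full BPI is given. With Day 7 blank in that row, nothing in the table prompts for these items at the Day 7 call, although the endpoint text requires them.

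The loss would be permanent. Under Section 8.1 participants answer for the previous 24 hours, so a later call cannot supply the Day 7 values. The multiple imputation in Section 9.4.1 would have no observed Day 7 interference scores from which to build a model.

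There is also an effect on testing. Section 9.4.3 lets testing pass to the next set only if the current one reaches significance. A set without data cannot do so, and the sequence would end there.

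**Working it through.** No power, sample-size or alpha figure bears on this point. The check is a cell-by-cell match of the schedule to the endpoints.

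**1. Reading the synopsis row.** The header has 8 cells (a label and seven days) and the BPI row has 8 cells (a label and seven day cells), so the row is well formed. The marks are in the third and seventh day cells, and the header puts those at Day 3 and Day 14. Read the same way, the opioid row falls on all seven days and the masking row on Day 1. Both agree with the endpoint text.

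**2. Setting schedule against endpoints.**

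| Item | Days required | Where required | Synopsis BPI row |
|---|---|---|---|
| Interference | 3 | Sections 1.1 and 3; set 3 in 9.4.3 | marked |
| Interference | 7 | Sections 1.1 and 3; set 5 in 9.4.3 | blank |
| Current and least pain | 3 | Sections 1.1 and 3 | marked |
| Current and least pain | 7 | Sections 1.1 and 3 | blank |
| Full BPI | 14 | no endpoint | marked |

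**3. Does Section 1.3 settle it?** The BPI row there has three marks, but its cells are shifted against the header in the machine-read text.

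- By the printed header, the marks fall on Days 2, 7 and 8.
- If the consent mark is taken as Day 0, they fall on Days 3, 8 and 14.
- The opioid row has 8 marks for 7 assessment days, and the masking mark shares a column with consent although Section 8.1 puts masking on Day 1.

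Neither alignment gives both Day 3 and Day 7, and neither can be trusted. Section 1.3 as supplied neither confirms nor removes the inconsistency.

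**4. What would be affected if the synopsis table were followed.**

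- Lost: Day 7 interference, and Day 7 current and least pain.
- Untestable: set 5.
- Later sets: 13 − 5 = 8 (sets 6 to 13). They lose their place in the error-controlled sequence only if sets 1 to 4 were all significant; otherwise the sequence would already have stopped.
- Still analysed: Section 9.4.3 assesses individual time points regardless of earlier results in the sequence. Sets 7 to 13 are all outcomes at individual time points, so they would be reported, without sequence control. Set 6, cumulative awakenings over the first week, is the only later set that is not such an outcome.
- Unaffected: the primary endpoint (average pain has its own row), cumulative opioid use, Day 3 interference (marked) and set 4 (worst pain has its own row).

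**The case against.** The strongest reply is that the evidence is the position of one mark in a table read by a program. The row is well formed. However, every other row is either fully filled or has a single mark in the first day cell, so no other row tests whether a sparse mark further along was placed correctly. This stands, and the source page should be looked at first.

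A second reply is that the intended design is not in doubt. The endpoint lists, the objectives table and the serial testing table all say Day 7, one of those statements is just above the table in the synopsis, and a Day 7 call takes place anyway. This also stands. It makes a clerical slip the likely explanation, but it does not make the table right. The general list of evaluation days in Section 8.1 does not rescue it either, because it ties no instrument to a day.

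Three stronger readings are tempting, and the documents do not support them:

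- *No participant will have Day 7 interference data.* This assumes that staff follow one summary table and ignore every explicit Day 7 statement. The case report form and call scripts are not in the documents, so no data loss is shown.
- *The Section 1.3 schedule is also wrong.* Its layout is too garbled to say so, and under the printed header its BPI row includes Day 7.
- *The Day 7 pain and opioid tests would be lost.* Those items have their own rows on Day 7, and Section 9.4.3 assesses them whatever happens earlier in the sequence.

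**Conclusion.** The inconsistency is real on the text as supplied. The synopsis table schedules the full BPI on Days 3 and 14, the endpoints need it on Days 3 and 7, and nothing uses it on Day 14.

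Its size is modest. It touches one lower-order set in the testing sequence and other secondary endpoints, not the primary or key secondary results. The consequences are conditional on two things: that callers or the case report form follow the synopsis table and, for the effect on sets 6 to 13, that sets 1 to 4 are all significant. The finding also assumes that the machine-read row matches the printed page. It should still be corrected, because missed Day 7 scores cannot be recovered.

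**What to change.** 1. Check the BPI row of the synopsis table on the source page.
2. If it reads as supplied, correct it to show Days 3 and 7.
3. Confirm that the BPI row in Section 1.3 shows the same days, and change it only if it does not.
4. Keep a Day 14 BPI only if an endpoint is written that uses it.
5. Check the case report form and call scripts against the reconciled schedule, preferably before randomization starts.

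The cost is a correction to one table, possibly two, and a form check. No contact is added, because the Day 7 call already takes place. If the Day 14 BPI is dropped, the number of full BPI administrations shown in the synopsis table stays at two.
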